#### Confirmatory Response Rate by RECIST v1.1 or GCIG CA-125 Criteria

The endpoint of ORR assessed by RECIST or GCIG CA-125 criteria is defined as a best confirmed response of CR or PR using RECIST v1.1 or a confirmed response per GCIG CA-125 criteria. The endpoint of CA-125 response rate is defined as a 50% reduction from baseline in CA-125 measurement as assessed by GCIG criteria and it is further described in Appendix A.

Only patients with elevated levels of CA-125 baseline value at least twice the upper limit of normal (>70 iU/mL) will qualify to have a response per GCIG CA-125 criteria.

The combined ORR will be assessed as indicated in Table 2.

Table 2: Overall Response by RECIST v1.1 and GCIG CA-125 Criteria Error! Reference source not found.		
RECIST Response	GCIG CA-125 Response	RECIST + GCIG CA-125 Combined
CR (requires normalization of CA-125)	CA-125 within normal range	Response
PR	Response	Response
PR	No Response	Response
SD	Response	Response
SD	No Response	No Response
PD	Response	No Response
PD	No Response	No Response

CR= Complete Response, PD = Progressive Disease, PR= Partial Response, SD = Stable Disease.

The response rate will be summarized with frequencies and percentages in addition to 95% Confidence Interval (CI) of the proportion using Clopper-Pearson methodology.

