- ^f = Includes hemoglobin, hematocrit, WBC and differential (with ANC), and platelet count. Blood will be analyzed by a local laboratory and must be reviewed by the investigator prior to dosing with rucaparib.
- ^g = To be performed ≤ 14 days prior to the first dose of rucaparib.
- ^h = Includes total protein, albumin, creatinine, BUN or urea, total bilirubin, ALP, ALT, AST, total cholesterol, glucose, sodium, potassium, chloride, CO₂, calcium, and phosphorus. Blood will be analyzed by a local laboratory.
- ⁱ = Serum β -hCG (evaluated by local laboratory) will be performed only on women of childbearing potential at the following time points: ≤ 3 days prior to the first dose of rucaparib, ≤ 3 days prior to Day 1 of every cycle from Cycle 2 and beyond, and at the End-of-Treatment Visit.
- ^j = CA-125 as measured by a local laboratory.
- ^k = Includes dipstick for protein, glucose, blood, pH, and ketones. If dipstick findings are abnormal, then a microscopic evaluation will be performed to assess the abnormal findings.
- ^l = Tumor assessments to consist of clinical examination and appropriate imaging techniques (preferably CT scans of the chest, abdomen, and pelvis, with appropriate slice thickness per RECIST); other studies (MRI, X-ray, PET, and ultrasound) may be performed if required. The same methods used to detect lesions at baseline are to be used to follow the same lesions throughout the clinical study. Tumor scans will be collected and sent for evaluation by independent radiology review.
- ^m = Tumor scans to be performed within 7 days prior to the start of Cycles 3, 5, and 7, and then within 7 days prior to the start of every third cycle of treatment thereafter, beginning at Cycle 10. If initial CR or PR is noted prior to start of Cycle 7 or beyond, confirmatory scans must be performed 4–6 weeks later.
- ⁿ = A mandatory archival tumor biopsy will be collected from newly enrolled patients and from previously enrolled patients who provide additional consent. Refer to the Pathology Charter for detailed sample handling instructions. May be collected at Any time during study.
- ^o = AEs are recorded from time of signing of informed consent through 28 days after last dose of rucaparib. Ongoing SAEs should be followed until resolution.
- ^p = PK sample to be collected approximately 12 h after the last dose, but prior to the next dose (i.e., typically 5–10 min prior to dosing).

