11.2.4.1 Overall Response Rate - Primary Endpoint (Part 2)

A primary efficacy endpoint in Part 2 of the study (ORR) is the best overall response recorded from the start of the treatment until disease progression or recurrence. The ORR will be summarized for the tumor-evaluable population enrolled in Part 2 with frequencies and percentages.

11.2.4.2 Secondary Analyses and Endpoints in Part 2 and 3

11.2.4.2.1 ORR per RECIST v 1.1 and Gynecologic Cancer Intergroup (GCIG) CA-125 Criteria (Part 2)

The proportion of patients with the best response by RECIST v 1.1²⁷ of ‘Complete Response’ or ‘Partial Response’ or response according to the GCIG CA-125^{28,29} criteria will be summarized with number of patients and percent and for each response category.

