## 12.3 Exploratory Efficacy Analyses

### 12.3.1 To explore the association between genomic alterations identified in tumor tissue and clinical outcome (Part 1, 2, and 3)

No formal statistical analysis of efficacy was performed for Part 1 and Part 3, thus genomic data and tumor response data will be presented in patient listings.

For Part 2A and Part 2B, the proportion of patients with the best confirmed response by RECIST Version 1.1 of CR or PR and the proportion of patients with best confirmed response by RECIST Version 1.1 or response according to the GCIG CA-125 criteria were summarized by BRCA

mutation type (BRCA1 or BRCA2). The ORR will be summarized with frequencies and proportion together with 95% Confidence Interval (CI) of the proportion using Clopper-Pearson methodology for each subgroup.

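### The combined RECIST/CA-125 response has two rules that disagree for a CA-125 responder with RECIST progression, and the scoring table has no row for RECIST not evaluable

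*SAP*

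**What the plan says.** SAP 12.1 describes a combined endpoint for Parts 2A and 2B. In words, a combined responder "is defined as a best confirmed response of CR or PR using RECIST v1.1 or a confirmed response per GCIG CA-125 criteria". The CA-125 arm is open only to patients whose baseline reaches twice the upper limit of normal (ULN), which the SAP glosses as above 70. The section then states: "The combined ORR will be assessed as indicated in Table 2".

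Table 2 cross-classifies RECIST response and CA-125 response. Its stable-disease row reads "SD Response Response" and its progression row reads "PD Response No Response". The legend lists every RECIST category that the table covers: "CR= Complete Response, PD = Progressive Disease, PR= Partial Response, SD = Stable Disease". The RECIST part of the same section also reports a not-evaluable category.

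The endpoint is described in two other places:
- SAP 12.3.1, for the rates by BRCA1 and BRCA2: "proportion of patients with best confirmed response by RECIST Version 1.1 or response according to the GCIG CA-125 criteria".
- Protocol 11.2.4.2.1: best RECIST response of CR or PR "or response according to the GCIG CA-125" criteria.

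Neither cites Table 2 or excepts progression. On measurement, a footnote to protocol Table 11 says "CA-125 as measured by a local laboratory".

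SAP 11.1 attaches the CA-125 analysis to the primary endpoint, while SAP 11.2 lists the combined rate as secondary.

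**The concern.** The wording and the table classify some patients differently. Suppose a patient has RECIST PD as best response and a confirmed, qualifying CA-125 response. The sentence makes her a responder and the table does not. If she is RECIST NE, the sentence makes her a responder and the table is silent. A programmer who follows Table 2 for the overall rate and SAP 12.3.1 for the by-gene rates could report BRCA1 and BRCA2 responders that do not add up to the overall count.

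Under the either/or wording, a patient who progressed on imaging can count as a treatment success. The study is open-label, so an unresolved choice between the rules could be settled with the results in view.

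**Working it through.** **The plan's own figure.** The combined rate gets a 95% Clopper-Pearson interval, the method behind the Part 2B table in SAP 3.2.1.3. With lower limit Beta⁻¹(0.025; x, n−x+1) and upper limit Beta⁻¹(0.975; x+1, n−x) at n=40:
- 12/40: 16.6 to 46.5 (plan: 17, 47)
- 16/40: 24.9 to 56.7 (plan: 25, 57)
- 20/40: 33.8 to 66.2 (plan: 34, 66)

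The table is reproduced.

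**The two rules, cell by cell.** A CA-125 response here means confirmed, with a qualifying baseline.

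| RECIST | CA-125 | Text of SAP 12.1 | Table 2 |
|---|---|---|---|
| CR | within normal range | Response | Response |
| CR | not normalized | Response | no row |
| PR | response | Response | Response |
| PR | no response | Response | Response |
| SD | response | Response | Response |
| SD | no response | No response | No response |
| PD | response | **Response** | **No response** |
| PD | no response | No response | No response |
| NE | response | **Response** | **no row** |
| NE | no response | No response | no row |

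The rules contradict each other in one cell (PD with CA-125 response). In one further cell the text counts a CA-125-only responder and the table gives no answer (NE with CA-125 response).

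**Can these cells be occupied?** With 21-day cycles and no delays, Cycle 3 starts on day 2×21+1 = 43, so the first scan falls on about days 36 to 42. Cycle 5 starts on day 4×21+1 = 85, so the second scan falls on about days 78 to 84. SAP 12.1 keeps SD followed by PD as SD only if the SD was seen at least 49 days after treatment start. SD at the first scan and PD at the second does not meet that condition. CA-125 is drawn on Day 1 of each cycle (days 22, 43, 64), so a fall and a second value supporting it can both precede that PD. For NE, protocol Appendix A assigns it when target lesions were not evaluated and non-target disease has not progressed, which can happen in a patient who has been scanned.

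**Size per patient.** 1/41 = 2.4 points and 1/40 = 2.5 points. In a gene subgroup of m patients it is 100/m points, which is larger. The documents do not give m.

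**Illustration.** Let k be the number of CA-125 responders with RECIST PD or NE. The documents do not give k. Assume Table 2, with NE scored as non-response, gives about 73%, borrowed from SAP 3.2.1.3 only as a starting point (0.73×40 = 29.2; 0.73×41 = 29.9).

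| k | n=40, text rule (95% CI) | n=41, text rule |
|---|---|---|
| 0 | 29/40 = 72.5% (56.1 to 85.4) | 30/41 = 73.2% |
| 1 | 30/40 = 75.0% (58.8 to 87.3) | 31/41 = 75.6% |
| 2 | 31/40 = 77.5% (61.5 to 89.2) | 32/41 = 78.0% |
| 4 | 33/40 = 82.5% (67.2 to 92.7) | 34/41 = 82.9% |

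**Threshold.** Twice the ULN equals 70 only if the ULN is 70/2 = 35. For an assumed local ULN of 30 the threshold would be 60, and for 40 it would be 80. The documents give no local limits. In addition, one form includes the boundary value and the other excludes it.

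**The case against.** The best defence is that the SAP says which rule operates. The sentence is a general definition, Table 2 follows at once as the scoring algorithm, and the other two statements are short descriptions of the same endpoint. For the PD cell in SAP 12.1 this is a fair reading. It does not reach SAP 12.3.1 or the protocol, which never mention the table, and it cannot settle NE, which the table omits.

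The NE gap is also narrow. The SAP's examples of NE are patients who stop or die before any tumour assessment. Most of these leave the efficacy population, which needs a post-baseline disease assessment, unless CA-125 counts as one. The safety-population summary is stated for the RECIST endpoint and not plainly for the combined rate. What remains is mainly NE in scanned patients.

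Three stronger readings are tempting, and the documents do not support them:
- **That the gap between 47% (RECIST) and 73% (combined) is at stake.** SD with a CA-125 response counts under both rules, so those patients are not in dispute. The two figures come from a pooled group across two studies, given without denominators, and no part of the gap is shown to be PD or NE.
- **That any CA-125 fall counts under the text.** SAP 12.1 requires a confirmed response and a qualifying baseline.
- **That the CA-125 arm has no cut at progression.** SAP 12.1 refers the CA-125 definition to its Appendix A, which was not in the text available for this review and may deal with timing.

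**Conclusion.** The point stands as a conflict of definition with a gap in the scoring table. PD with a CA-125 response is a response in three statements of the endpoint and a non-response in Table 2. NE with a CA-125 response is a response in the wording and unscored in the table.

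The effect is 2.4 or 2.5 points per affected patient in the overall rate, and zero if there are none. It is limited to the combined rate, overall and by gene, which is reported descriptively with confidence intervals. The conclusion assumes that nothing in SAP Appendix A overrides the either/or wording for PD or NE.

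A reader might infer that the primary result is in doubt. It is not. The primary analysis is confirmed RECIST response, and the Simon rule and both sample sizes rest on RECIST response or on interval width. The change is worth making because it is cheap and stops patients who progressed on imaging from counting as responders.

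**What to change.** 1. In SAP 12.1 and 12.3.1, define the combined responder as a responder per Table 2 and delete the either/or wording.
2. Record in the SAP that this replaces the wording of protocol 11.2.4.2.1. Protocol 11.2.1 already expects departures from its methods to be described and justified there.
3. Add NE rows to Table 2. For example, NE with a CA-125 response is a non-response in the main analysis and a response in a sensitivity analysis. Either assignment is defensible if fixed beforehand. NE without a CA-125 response is a non-response.
4. Add a row for RECIST CR without CA-125 normalization. Protocol Appendix A requires marker normalization for CR and appears to make such a patient a PR, which Table 2 scores as a response. The row should say so.
5. State the baseline threshold as at least twice the ULN of the laboratory that ran the sample, and drop the fixed value of 70.

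The cost is SAP wording, one derivation and the collection of local CA-125 limits where these are not already held. The downside is that the combined rate may fall slightly.

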### **12.1.1 Primary Efficacy Subgroups**

The primary endpoint will be explored in the following subgroups:

- BRCA mutation type (germline, somatic)
- Progression-free interval to the last platinum-based regimen prior to rucaparib (<6 months, 6 to 12 months, and >12 months).
- Platinum-response status (sensitive, resistant, refractory) relative to most recent platinum containing regimen., where status is defined as
  - Refractory: Best response of PD and PD occurs during or up to 2 months after regimen
  - Resistant: PD 0-<6 months after last platinum with best response other than PD
  - Sensitive: PD  $\geq$ 6 months after last platinum

This may only be presented descriptively if there are few patients in a proposed subgroup.

## 12.2 Secondary Efficacy Analyses

The secondary endpoints are to further explore clinical benefit in terms of response in cancer antigen and duration of response.

### 12.2.1 Progression-free Survival (Part 2)

PFS will be calculated as 1+ the number of days from the date of first dose of study drug to disease progression or death, due to any cause, whichever occurs first. Patients without a documented event of progression will be censored on the date of their last adequate tumor assessment (i.e., radiologic assessment) or date of first dose of study drug if no tumor assessments have been performed. PFS will be summarized using Kaplan-Meier methodology.

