9.9 Long-term Follow-up

For Part 2B patients only:

- All Part 2B patients discontinued from treatment, regardless of reason, should be followed for survival, subsequent anti-cancer treatments, and secondary malignancy monitoring every 12 weeks [± 7 days] until death, loss to follow-up, withdrawal of consent from study, or study closure, whichever happens first. Follow-up can be performed via the telephone. Diagnosis of any secondary malignancy requires appropriate documentation (i.e., laboratory and/or pathology reports).
- Tumor scans (using the same methodology as was used at screening) for any patient who discontinued from study treatment for reason other than disease progression or death to be performed within 7 days prior to the start of every 9 weeks until radiologically confirmed disease progression, death, or initiation of subsequent treatment. Patients who have been on study at least 18 months may decrease the frequency of tumor scans to every 16 weeks [± 14 days]

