9.10.5 Efficacy Evaluations

9.10.5.1 Tumor Assessments

For Part 1 and Part 2, tumor assessments will be performed at screening, within 7 days prior to the start of Cycles 3, 5, and 7, within 7 days prior to the start of every three cycles thereafter, beginning with Cycle 10, and at the end-of-treatment visit.

For Part 2B, tumor assessments will also be performed during the long-term follow-up period for any patient who discontinued from study treatment for reason other than disease progression or death, within 7 days prior to the start of every 9 weeks until radiologically confirmed disease progression, death, or initiation of subsequent treatment. Patients who have been on study at least 18 months may decrease the frequency of tumor scans to every 16 weeks (± 14 days).

For Part 3, tumor scans will be performed at screening, within 7 days prior to the start of Cycles 3, 5, and 7, and within 7 days prior to the start of every three cycles thereafter, beginning with Cycle 10.

If initial CR or PR is noted at Cycle 7 or beyond, confirmatory scans must be performed 4–6 weeks later. Tumor response will be interpreted using RECIST Version 1.1 ([Appendix A](#)).

Tumor assessments should consist of clinical examination and appropriate imaging techniques (preferably CT scans of the chest, abdomen, and pelvis with appropriate slice thickness per RECIST); other studies (MRI, X-ray, PET, and ultrasound) may be performed if required. The same methods used to detect lesions at baseline are to be used to follow the same lesions throughout the clinical study. Investigators should perform scans of the anatomical sites that, in their judgment, are appropriate to assess based on each patient's tumor status. For patients in Part 2 and Part 3, tumor scans will be collected for possible evaluation by independent radiology review.

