6. To assess progression-free survival (PFS) in the OC population (Part 2 only)	6. PFS defined as the time to first occurrence of disease progression per RECIST v1.1 or death
7. To evaluate survival (Part 2B only)	7. Overall survival (OS)
Exploratory Objectives	Exploratory Endpoints
1. To explore the relationship between the PK of oral rucaparib and the potential changes in QT/QTc interval (Part 1 only)	1. QT/QTc interval correlated with plasma concentrations of oral rucaparib
2. To profile circulating metabolites of oral rucaparib at steady state at the RP2D (Part 1 only)	2. Metabolic profile in the Day 15 plasma samples
3. To explore the association between genomic alterations identified in tumor tissue and clinical outcome (Part 1, 2, and 3)	3. Mutational status of BRCA1/2 and other homologous recombination genes. Genomic scarring/ loss of heterozygosity (LOH) assessment in tumor tissue and response by RECIST v1.1 and/or tumor markers (ie, CA-125)

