## **13 STATISTICAL/ANALYTICAL ISSUES**

### **13.1 Handling of Dropouts or Missing Data**

All data will be used to their maximum possible extent but without any imputations for missing data. All time to event endpoints are censored and the rules for deriving the censoring value is described in more detail under each one of the time to event endpoints.

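### The PFS censoring sentence omits death and, applied literally, censors deaths that the definition counts as events; the handling of new anticancer therapy in Part 2B is also unstated

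*SAP*

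**What the plan says.** SAP 12.2.1 runs PFS from first dose "to disease progression or death, due to any cause, whichever occurs first". SAP Table 1 agrees: "PFS defined as the time to first occurrence of disease progression per RECIST v1.1 or death". Table 1 of the protocol defines the endpoint in the same way.

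The censoring sentence that follows in SAP 12.2.1 is: "Patients without a documented event of progression will be censored on the date of their last adequate tumor assessment". A patient with no tumor assessment is censored at first dose. Death is not mentioned. Protocol 11.2.4.2.3 has the same sentence.

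No other section settles the matter. SAP 13.1 says that "the rules for deriving the censoring value is described in more detail under each one of the time to event endpoints", which sends the reader back to 12.2.1.

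For Part 2B patients who stop treatment without progression, Protocol 9.9 continues scans "until radiologically confirmed disease progression, death, or initiation of subsequent treatment". Patients in that cohort "should be followed for survival, subsequent anti-cancer treatments, and secondary malignancy monitoring every 12 weeks". Part 2A has no such long-term follow-up. Neither document says what a new anticancer therapy does to PFS.

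**The concern.** Consider a patient who dies with no progression on any scan. The definition makes her an event on her date of death. The censoring sentence makes her a censored observation at her last scan. Two programmers working from the same paragraph could produce different curves.

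Such patients are foreseeable. Appendix A of the protocol describes patients who stop treatment for deteriorating health without objective progression. The neighboring sections do not help a programmer. The OS section names death in its censoring rule, while the duration-of-response section counts only progression as an event.

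The second gap concerns Part 2B patients who start another therapy before progression. Their scans end but their deaths are still recorded. If deaths count, a switcher who dies is an event at death, however late, and a switcher who survives is censored at her last scan. Her censoring date then depends on what happens to her later, which Kaplan-Meier does not allow for.

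The median PFS and, under Protocol 11.2.1, the 3-, 6-, 9- and 12-month PFS rates are at stake.

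**Working it through.** The documents give no PFS target, event count or power, so there is no planned figure to reproduce. Every rate below is an assumption.

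**Step 1. Literal rule, closed form.** Let the true median be 8 months with exponential times, and let a share *d* of PFS events be deaths without documented progression. The total hazard is ln 2 / 8. Censoring those deaths leaves (1 − *d*) of that hazard, so the estimated median is 8 / (1 − *d*) and estimated 12-month PFS is 0.5^(12(1 − *d*)/8).

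| *d* | Median (months) | 12-month PFS |
|---|---|---|
| 0 (true) | 8.0 | 0.5^1.5 = 0.354 |
| 0.05 | 8/0.95 = 8.4 | 0.5^1.425 = 0.372 |
| 0.20 | 8/0.80 = 10.0 | 0.5^1.2 = 0.435 |

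**Step 2. Simulation on the protocol's scan schedule.** On treatment, scans fall "within 7 days prior to the start of Cycles 3, 5, and 7" and then every third cycle from Cycle 10. With 21-day cycles that is weeks 6, 12 and 18, then every 9 weeks. There were 100,000 patients per scenario. The assumptions were:

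- median PFS of 8 or 10 months;
- 0% to 20% of events as deaths without progression;
- new therapy before progression at 0%, 2% or 5% per month, or in 20% of patients just before progression;
- a death hazard after progression of 0.05 or 0.15 per month;
- a data cut at 15 or 36 months.

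The reference keeps scanning after new therapy and counts deaths. The table shows 12-month PFS for a median of 8 months and a death hazard of 0.15; the cut is censoring at the last scan before new therapy.

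| Scenario | Reference | Deaths censored | Deaths counted, no cut | Deaths counted, cut |
|---|---|---|---|---|
| *d* = 10%, no new therapy, 15 months | 0.391 | 0.491 | 0.391 | 0.391 |
| *d* = 5%, 5% per month switch, 15 months | 0.392 | 0.469 | 0.321 | 0.389 |
| Same, 36 months | 0.403 | 0.473 | 0.437 | 0.400 |
| *d* = 5%, 20% switch just before progression, 15 months | 0.393 | 0.539 | 0.409 | 0.460 |
| Same, 36 months | 0.399 | 0.540 | 0.438 | 0.467 |

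**Step 3. Results over all scenarios.**

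- *Deaths censored:* 12-month PFS is overstated every time, by 1.8 to 14.6 points without prognosis-driven switching and by up to 21 points with it. These shifts exceed those in step 1 because deaths between true progression and the next scan are lost as well.
- *Deaths counted, no new therapy before progression:* the estimate equals the reference.
- *Deaths counted, no cut at new therapy:* 12-month PFS is understated by 1.2 to 7.8 points when switching is unrelated to prognosis and data are cut at 15 months. It is overstated by 1.2 to 4.7 points at 36 months, and by 1.2 to 7.0 points when 20% switch just before progression.
- *Deaths counted, cut at new therapy:* within 1 point of the reference when switching is unrelated to prognosis, but about 4 to 8 points too high when 20% switch because progression is imminent.

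The sign change without a cut has a simple cause. With short follow-up, switchers who die add events while surviving switchers leave the risk set early. With long follow-up, most switchers die late and count as progression-free until then.

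**The case against.** The strongest reply is that the censoring sentence is only loosely worded. The sentence before it and the objectives tables of both documents count death, so a sensible programmer would too. That is probably the intent, and a reader should not infer that the sponsor means to censor deaths. But the sentence is the operative rule, and SAP 13.1 points to it. The objection makes the error less likely to be carried out; it does not make the sentence correct.

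A second reply is that the new-therapy gap is narrow. This largely stands. A Part 2B switcher who is alive without progression is already censored at her last scan, before the new therapy. Only Part 2B patients who switch before progression and later die are affected.

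A third reply is that sampling error dominates. With 30 events and a median of 8 months, an exponential approximation gives 8·exp(±1.96/√30), or 5.6 to 11.4 months; with 40 events it gives 5.9 to 10.9. The shifts in median from 8 to between 8.4 and 10.0 lie inside both intervals. That limits the consequence, but it does not justify a systematic error that a few words remove.

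A reader might infer that PFS is overstated whichever way the rule is read. The documents do not support this. They fix no PFS data-cut date and give no reasons for switching, and with deaths counted the direction depends on both. Nor do they support the inference that censoring at new therapy cures the problem: when switching reflects deterioration, such censoring is itself informative.

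**Conclusion.** The censoring sentence is wrong as written in both documents. Applied literally it overstates PFS, and that direction follows from the rule itself. The size does not: 8.4 to 10.0 months against 8 rests on exponential times, an assumed median and an assumed 5% to 20% share of deaths without documented progression.

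The missing rule for new therapy is a separate and smaller gap, confined to Part 2B. It can bias PFS up or down, and the choice between the two usual handlings is a choice of estimand.

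The consequence is limited. PFS is a secondary Kaplan-Meier summary in a single arm, with no test or threshold, and the Part 2 decisions rest on ORR.

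**What to change.** 1. In SAP 12.2.1, restrict the censoring sentence to patients with neither documented RECIST progression nor death, and leave the censoring date as it is. Note the correction to the identical sentence in Protocol 11.2.4.2.3.
2. For Part 2B, state which handling of new anticancer therapy is primary: censoring at the last adequate scan on or before its start, or counting all later deaths as events. Report the other as a sensitivity analysis and present neither as free of bias.
3. Report how many Part 2B patients started new therapy without progression, and how many of them later died, so that readers can see how much the choice matters.

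The cost is a few words, one added rule and one extra Kaplan-Meier run. Subsequent treatments and survival are already collected in Part 2B. Censoring at new therapy leaves fewer events; counting later deaths brings in deaths after a gap in scanning.
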